5.6 Control Condition

Participants who are randomized to the control condition will engage in one CTR session delivered via Zoom video-counseling. Approximately one week prior to the scheduled session, a box containing a home oral fluid HIV-test (OraQuick) kit will be mailed by the study team to the address provided by each participant. The participants will be instructed to have the kits with them at the time of the scheduled session, but not to use them prior to the session. The CTR session will begin by discussing the participants' perceptions of risk,, delivering the test result, and prevention planning, which will be followed by linkage and referrals to local services. During the session, the remotely located counselor will instruct the participant on how to self-test using the home HIV-testing kits mailed to them. The counselor will observe the testing, ensure they can read and interpret the results correctly, and prevention planning will be centered on the results of the HIV testing.

For both conditions, participants who receive an HIV-positive result will be counseled on the need for timely linkage to care. The counselor will arrange a time within 1 week of the initial session to conduct a second video session for participants who have preliminary positive results. During this session, new preliminary positives will be directly linked to medical care by connecting them with a medical care contact in their local area. Study staff will follow-up with them on the next business day to ensure that contact was made with a local facility closest to where the participant lives or with a medical care agency. The participant would be contacted at least three times: (1) to confirm an appointment was scheduled; (2) to confirm the appointment was attended; and (3) to report confirmatory results.

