For preliminary positive results for any participant, at the end of the video CHTC + Relationship Skills or CTR + Relationship Skills session, the participant will be counseled on the need for timely linkage to care. Within 48 hours, the counselor will then send a confidential email to the participant(s) individually providing the contact information for providers in their area who can provide confirmatory testing and linkage to care. Then within 1 week of the session, study staff will follow up with the participant(s) over the phone or Zoom to see if an appointment was made. If not, staff will urge participants to make an appointment as soon as they can and will emphasize the importance of confirmatory testing and linkage to care. Study staff will then follow up within 1 month of the session and 3 months to (1) confirm an appointment was scheduled, 2) to confirm the appointment was attended, 3) to report confirmatory results, and 4) assess linkage to care.

Satisfaction survey: Within one week of the CHTC + Relationship Skills or CTR + Relationship Skills session, each participant will receive an email asking them to complete a short satisfaction survey: the survey will include questions regarding satisfaction with the home testing process, logistics (i.e., length of session), content of session, and reactions to testing process (i.e. ease, comfort), in addition to willingness to utilize the intervention in the future. If the participant's partner also took part in the session, they are also sent a satisfaction survey.

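### Sections 5.6 and 6.6 describe different follow-up after a preliminary positive HIV result without cross-reference, and the Phase III text of 6.6 does not name the control session

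*Protocol*

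**What the plan says.** Section 5.6 of the protocol is headed as the control condition, but its text on positive results is general: "For both conditions, participants who receive an HIV-positive result will be counseled on the need for timely linkage to care". It then sets out four steps.

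- A further session: "The counselor will arrange a time within 1 week of the initial session to conduct a second video session".
- What happens in that session: "new preliminary positives will be directly linked to medical care by connecting them with a medical care contact in their local area".
- A check afterwards: "Study staff will follow-up with them on the next business day to ensure that contact was made with a local facility".
- Later contact: "The participant would be contacted at least three times", to confirm that an appointment was scheduled, that it was attended, and what the confirmatory result was. No dates are attached.

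Section 6.6 has its own positive-result text for Phase III. It opens with results obtained "at the end of the video CHTC + Relationship Skills or CTR + Relationship Skills session". It continues: "Within 48 hours, the counselor will then send a confidential email to the participant(s) individually providing the contact information for providers in their area". Study staff then check by phone or Zoom within 1 week whether the participant has made an appointment, and press for one if not. Further contacts follow within 1 month of the session and at 3 months, for the same three purposes as in 5.6 plus an assessment of linkage. The Phase II text of 6.6 gives the same steps for the pilot's couples session.

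Section 6.4 lists linkage to care, self-reported within three months of diagnosis, among the data collected for incident positives. Section 12.3 describes learning of a positive result as the greatest emotional and physical risk to participants, and provides that everyone with a positive result receives a full list of local providers.

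**The concern.** Two parts of the same protocol tell staff what to do after the same event, and they do not tell them the same thing. The main difference is who makes the link to care and how. In 5.6 the study connects the participant to a provider during a second counselor session. In 6.6 the participant receives contact details by email, makes the appointment, and is checked on by staff.

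The scope is also uneven. The heading of 6.6 mentions CTR, which suggests that the control session is included, but its Phase III text begins with the intervention-arm index partner and its positive-result paragraph names only the two intervention session types. As written, control participants are covered by 5.6 alone and intervention participants by both sections.

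At stake, first, is participant safety: participants may be as young as 15, are seen only remotely, and may be enrolled without parental involvement. Second is consistent conduct across arms, with a possible secondary effect on the linkage data.

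**Working it through.** There is no figure to reproduce. The check sets the Phase III texts of the two sections side by side and asks, for each element, whether staff could satisfy both.

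| Element | Section 5.6 | Section 6.6, Phase III | Compatible? |
|---|---|---|---|
| Stated scope | Both conditions | The two Relationship Skills sessions | Overlap in the intervention arm; control in 5.6 only |
| Counseling on timely linkage | Yes | Yes | Same |
| First written step | None by email | Counselor's email within 48 hours | Could be added; 5.6 is silent |
| Contact within 1 week | Counselor, second video session | Study staff, phone or Zoom | Both could be done; actor and content differ |
| How the link is made | Direct connection to a local care contact | Provider details sent; participant books | Substantive difference |
| Next-business-day check | Yes, that contact was made | Not mentioned | Could be added; 6.6 is silent |
| Later contacts | At least three, undated | Within 1 month and at 3 months | Compatible |
| Purpose of later contacts | Scheduled, attended, confirmatory result | The same three, plus linkage | Compatible |

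**Timings.** The next business day, 48 hours and 1 week mark different events: on the natural reading, the check after the second session, the email after the first session, and the contact in the first week. They can all be met.

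**Number of contacts.** Section 6.6 gives one contact within 1 week, one within 1 month and one at 3 months: 1 + 1 + 1 = 3. This meets the minimum of three in 5.6.

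**Coverage by arm.** Section 5.4 offers CTR + Relationship Skills and CHTC + Relationship Skills only to the intervention arm, and 5.6 gives the control arm a single CTR session. The intervention arm is therefore covered by 5.6 and 6.6, and the control arm by 5.6 alone. The 48-hour email and the dated 1-month and 3-month contacts are written for one arm.

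**Reconciling text.** Neither section cites the other. The provider list in 12.3 applies to everyone with a positive result but does not say which pathway governs. The measures in 6.1 and 6.4 describe what is asked about linkage, not what staff do. Section 11.2 and the SAP do not mention linkage.

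**Bearing on the linkage data.** Section 5.4 places the intervention arm's initial session within four weeks of enrollment. The 1-month contact after it therefore falls at most about two months after enrollment (four weeks plus one month), before the 3-month survey that asks about linkage under 6.1. This assumes that surveys are timed from enrollment. A contact that checks on appointments could thus influence what is later reported, and it is dated for one arm only. The size of any effect cannot be computed, because the documents give neither an expected number of positives nor linkage rates.

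**The case against.** The strongest reply is that these texts overlap rather than conflict. Section 5.6 states one pathway for both conditions. Section 6.6 can be read as adding an email and supplying dates that 5.6 lacks. Nothing in 6.6 forbids a second session and nothing in 5.6 forbids an email. The provider list in 12.3 is common to both arms. Counselors also work to a manual and to existing HIV-testing protocols that are not among these documents and may already settle the matter.

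Much of this stands. A reader might infer that the sections contradict each other on every timing and on the number of contacts. They do not, as the table shows. A reader might also infer that the protocol assigns one pathway to each arm, or leaves control participants with none. It does neither: 5.6 covers both arms, and a difference in practice is an inference from the scope of 6.6, not something the protocol states.

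Three things survive. No text says that the steps are cumulative. A second counselor session with direct connection is not the same procedure as an emailed list with a staff check. The control CTR session is not named in the Phase III positive-result text of 6.6. An unseen manual might resolve these points in practice, but it would not make the protocol consistent.

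**Conclusion.** The point holds as an internal inconsistency in a safety procedure. The two sections differ on who makes the link to care and how, and the dated follow-up is written only for intervention sessions. Followed as written, the arms would receive different follow-up after a preliminary positive result.

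It is not a finding about power, type I error or the trial's main conclusions. A reader might go further and infer that differing staff action would be mistaken for an intervention effect. The documents do not support that: neither Section 11.2 nor the SAP specifies a between-arm comparison of linkage, linkage is not among the primary outcomes in 6.1, and it is collected only for incident positives. The supportable statement is that arm-specific follow-up could affect the linkage data.

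That cases will be few is an assumption. It rests on enrollment being limited to people who report negative or unknown status, since no expected number is given. The conclusion also assumes that no document outside the protocol and SAP has formally superseded either section.

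**What to change.** Reconcile 5.6 with the Phase III text of 6.6, and bring the parallel Phase II text of 6.6 into line or mark it as describing the completed pilot. The result should be one pathway, set out once and cross-referenced from the other places. It should state:

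- that it applies to both arms and to every session type, naming the control CTR session;
- that it applies to invited partners, who test in the couples session but, under Section 5.1, are not entered in SMART and have only limited data collected;
- for each step, who acts, by what means, and from which event the time is counted;
- whether the steps now listed separately are cumulative or alternatives.

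Which steps are kept is for the investigators to decide, and this review takes no position on it. The cost is a protocol wording change, with a matching edit to the counselor manual if it repeats either text. No change to sample size, survey schedule or analysis is needed.

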6.0 SURVEYS AND COUNSELING SESSIONS

6.1 Phase II and III Survey Measures

All surveys taken by participants are taken via a secure Alchemer link. During Phase III, this link will be distributed to them via SMART. For Phase II and III, our primary outcomes relate to the uptake of HIV prevention, conceptualized as self-report condomless sex, HIV testing, STI testing and PrEP knowledge, and efficacy and uptake. In addition, we will provide participants with kits to self-collect samples that will be mailed back and laboratory tested for STIs (syphilis, gonorrhea and chlamydia). The surveys will ask about the following information:

Demographics/Socioeconomic Characteristics:

- Age, race/ethnicity, sexual identity, housing status, history of incarceration, employment status, educational attainment, and income level.
- General sex and relationship history, including number of past partners stratified by female, male, transgender female, and transgender male partners, sexual intercourse with these partners, and length of relationships.

Primary Outcome Measures:

- *Powered Outcome:* The survey is powered on the 9-item HIV-related dyadic communication for men who have sex with men scale

- *Sexual Behaviors*: The survey will assess lifetime and past 1- or 3-month sexual intercourse, including the type and frequency of these sexual behaviors.
- *HIV, STI Testing and PrEP/PEP Use*: The survey will contain a detailed description of different HIV prevention strategies, specifically HIV testing, STI testing, PrEP, CHTC, nPEP. Awareness will be single item measures of whether the participant had heard of each of these prevention strategies (binary: yes/no). Willingness will be assessed with single item measures that ask whether the participant would be willing to use the biomedical prevention strategy if it were available for free (binary: yes/no). History and current use will be asked by asking participants their HIV and STI testing history and whether they have ever used or are currently using other prevention strategies (i.e., CHTC, PrEP, nPEP). For participants that test positive in the CHTC or CTR session, they will be asked a series of questions about linkage to care in the 1-month (Phase II) and 3-month (Phase III) follow-up survey. These questions include most recent HIV care, viral load/CD4 testing, ARV treatment uptake, and future HIV care.

Relationship Dynamic Measures:

- Surveys in this section will assess relationship satisfaction, commitment, experiences of relational closeness, and interpersonal violence.

Mechanism of Change Measures:

- In these surveys participants will be asked about risk communication with their partner, preferences for sexual health outcomes, any sexual agreements the couple may have (including breaking agreements), and general communication.

Psychosocial Measures:

- The survey will assess each participants' perception of their own HIV risk, perceived chances of success in life, anticipated HIV stigma, internalized heterosexism, everyday discrimination, family acceptance, sexual identity disclosure, depression and anxiety symptoms, and substance use.

Study Satisfaction Measures:

- Participants will be given a series of surveys that assess their satisfaction with the study, and give participants an opportunity to provide feedback on the relationship-skills session and the CHTC session.

At-Home HIV Testing Survey:

- In Phase III, participants are sent an HIV testing kit immediately after scheduling a session. It is possible that some participants who schedule a session will not actually complete the session. However, we would still like to know whether they completed the at-home HIV testing kit. If a participant is sent an HIV testing kit and does not complete a session within 45 days of enrollment, they will be sent a survey through SMART that will ask whether they took the test and the test result.

6.2 Phase I In-Depth Interviews (IDI)

Interviews for Phase I will be conducted via VSee, the HIPAA-compliant video-chat software that will also be used to deliver the intervention. The IDI will adopt a participatory methods approach, in which participants create timelines of their relationships. One way that participants can actively guide a qualitative interview process is through the use of activities in which participants are given guidelines or instructions by the researcher, but then take control of the

activity in a flexible and participant-centered approach. During the proposed IDI, participants will create a visual relationship timeline using virtual stickers to develop an overview of their dating and sexual history. The IDI follows a step-by-step process with discreet steps where participants place stickers on the timeline in response to questions about relationship dynamics, desires and communication. To construct the timeline, participants will add non-identifying nicknames for up to three “sexual and/or romantic partners” who were “significant or memorable” to the participant in some way; participants will define for themselves what “significant or memorable” means. The timeline begins with the age of when the participant first met the earliest partner and ended at the current age. Lines are added to show when and how long each relationship occurred. Participants are given flexibility on how to draw the lines in order to best represent the timeline of their relationship history (e.g. participants could choose to use different types of lines to represent different parts of the relationship, lines could stop and start again, lines for different people could overlap over the same time period). Participants then answer a series of questions on each relationship through an action-oriented process that involves participants applying stickers with predetermined labels to the timelines. Participants will first use “relationship tag” stickers with definition terms (e.g. partner, boyfriend, friends with benefits). Follow-up questions examine why terms were chosen, definitions of terms, relationship development and transitions, and relationship rules (e.g. monogamous vs. open relationship). Participants then answer the question, “How did you feel about this person when you were together?” by adding up to five positive and/or negative “emotion tags” for each partner (e.g. trusting, loved, disrespected, not myself). The timeline provides an anchor for discussion around relationship communication, negotiation and desires. Using the timeline, participants will be asked to define what a relationship is, their definition of a successful relationship, and their desires for future relationships. Participants will be asked to describe positive and negative experiences they have had in communicating within relationships. The IDI will ask participants to outline the communication skills they believe they have and the communication skills they desire to have. The IDI will end by asking the participants to describe their desired content and quality for a relationship-skills focused facilitated session. The goals and suggested outline of the session will be described, and participants will be asked to make suggestions for specific content areas.

6.3 Phase I Cognitive Interviews

After we complete the in-depth interviews, we will develop our intervention manual. The intervention manual is the counseling protocol which outlines the steps and scripts used for delivering the We Prevent condition. Following the intervention manual development, we enrolled a total of 8 YMSM to complete cognitive interviews with a study staff member who is based at the University of Michigan via VSee. During these interviews, the study staff member will walk the participant through each portion of the intervention manual. Participants will be asked to think aloud as they navigate through the intervention. The study staff member will note the participant’s behavior and any questions that they have regarding the content and flow; data will be collected via a standard cognitive interview notes form. As they navigate through the intervention, recordings will be made of any nonverbal behavior that could be important to take into consideration (e.g., frowns, sighs, or fidgeting). Recordings will be made of valuable data related to how they respond to each module (i.e., How long does it take participants to understand and respond to different modules?). These data will be used as exploratory indicators of content difficulty, attentiveness, and task-difficulty. After participants have completed the interview, they will be asked to reflect on whether the intervention met or exceeded their expectations and their HIV prevention and relationship needs. These data will be used to revise content and study procedures in preparation for implementation in Phases II and III. Consistent with our recruitment goals, we will enroll at least 50% racial/ethnicity minority YMSM (n = 4).

6.4 Phase II and III Measures

Demographics/Socioeconomic: Questions related to demographic characteristics were developed by the Adolescent Medicine Trials Network for HIV/AIDS Interventions (ATN) research program. Characteristics assessed in these questions include age, race, ethnicity, sex at birth, gender identity, sexual identity, income, education, employment, living situation, incarceration history, and internet access, and technology use.

General Sex and Relationship History: Questions related to history of relationships and sexual intercourse were developed by the Adolescent Medicine Trials Network for HIV/AIDS Interventions (ATN). Sex history questions assess age at first sexual intercourse, as well as lifetime and 3-month sexual intercourse with females, males, transgender females, and transgender males. Questions related to relationship history assess current relationship status, how participants identify their current relationship, length of current relationship, and the role of online technology in initiation of the current relationship.

Sexual Behavior and Risk: Sexual behavior and risk will be measured by questionnaires developed for and adapted from Project Nexus: Providing Online Counseling for Home-Based HIV Testing ([name] et al., 2017) and Project Stronger Together: A Dyadic Intervention to Improve Engagement in HIV Care Among Sero-Discordant Male Couples in Three US Cities ([name] et al., 2017). These questions focus on frequency of anal sex, condom use during anal sex, anal sex and condom use with outside partners.

HIV, STI Testing, and PrEP/PEP Use: HIV, STI Testing, and PrEP/PEP Use will be measured by questions adapted from the Adolescent Medicine Trials Network for HIV/AIDS Interventions (ATN) research program and Project Moxie: Providing Home-Based HIV Testing and Counseling for Transgender Youth ([name] et al., 2017). The baseline survey will include questions on lifetime HIV testing history. Follow-up surveys will repeat the questions from the baseline, and will also include questions on HIV testing in each 1- or 3-month period including test results. For Phase III, the HIV testing outcome will be: the proportion of YMSM tested for HIV 2 or more times at least 3 months apart in the 9-month follow-up period (“frequent tester”). As an additional analysis, we will also examine the proportions of participants who receive one HIV test.

The STI testing outcome is defined as the proportion of YMSM tested for STIs at least once in the follow-up period. At baseline, we will assess lifetime STI testing history and knowledge about STIs. We will ask participants what STIs they have been tested for, the date of their most recent STI test (if known), and whether a medical provider had diagnosed them with an STI. In the follow-up surveys, we will ask participants whether they had been tested for STIs in the past 1 or 3 months, and if so we will ask them to indicate what tests they had received and whether they had been diagnosed with an STI by their medical provider. For Phase II, participants will receive at-home STI test kits at baseline only. For Phase III, participants will receive at-home STI test kits at baseline and 6-month time points. The box contains instructions on how to collect the samples and how to mail them back to the study site. The samples will be laboratory tested for syphilis, gonorrhea, and chlamydia. We will measure the incidence of any STI in the follow-up period.

PrEP awareness will be a single item measure of whether the participant has heard of PrEP. At each follow-up assessment, PrEP-eligible HIV-negative YMSM will be asked whether they have begun using PrEP, and self-reported adherence to PrEP will be assessed at each follow-up.

Relationship Dynamic Measures: The relationship satisfaction measure will assess satisfaction with current relationship. Questions about partner's ability to provide support and companionship will be asked. Participants will also be asked questions about commitment, relational closeness, and interpersonal violence. These questionnaires will center on partner's fulfillment of intimacy needs, desire to have alternative relationships, and experiences of sexual, physical, or emotional violence. These measures will total to 45 questions.

Mechanisms of Change: These measures will include questions about communication between partners about sex and condom use, as well as questions about existing sexual agreements. Participant's attitude toward existing sexual agreements, such as commitment to the agreement and breaking of the agreement will also be assessed.

Psychosocial Measures: These measures will include questions HIV risk perception and anticipated stigma, and perceived changes of success in life. We will also assess experiences of stigma with questions about internalized heterosexism, everyday discrimination, family acceptance, and sexual identity disclosure. Depression, anxiety, and substance use will also be assessed in this section.

Linkage to HIV Care: For any incident HIV-positive individuals, we will also collect the following outcomes as indicators of linkage to care, per the recent recommendations of the Institute of Medicine [48]. These are measured within three months of HIV diagnosis via self-report [49], [50]: (1) attending at least one clinical care appointment, (2) having at least one CD4 test performed, and (3) having at least one viral load test performed. Onset of ART initiation, self-reported adherence to ART, and viral suppression are exploratory indicators, as we recognize that our follow-up period may not be a sufficient amount of time to see these changes. We will obtain guidance from the ATN on the feasibility of collecting biomarkers of viral suppression and conduct medical chart reviews for youth who are newly diagnosed.

Feasibility: In addition to the outcomes, the study will assess feasibility by examining (1) time to recruit YMSM to the intervention in both Phase II and III, and (2) rate of recruitment of YMSM expressing interest in participation. Acceptability of the intervention will be determined by analysis of data from a satisfaction survey on the intervention's acceptability. In addition, the percentages of YMSM who do not complete the either of the intervention sessions will be assessed. Adequate feasibility will entail recruiting and enrolling at least 5-6 YMSM and their partners per month and ensuring at least 80-90% retention rate.

